#### I.1.e. VISIT 2 (DAY 1)

Upon arrival, the patient will be administered the SDQ, the HAM-D6, , the CGI-I, the CGI-S, and the CHRT. Following completion of the scales, the remaining procedures listed in Table 3 should be completed.

#### I.1.f. VISIT 3 (DAY 2)

Upon arrival, the patient will be administered the SDQ, the HAM-D6, the MADRS, the CGI-I, the CGI-S, and the CHRT. Following completion of the scales, the remaining procedures listed in Table 3 should be completed.

#### I.1.g. VISIT 4 (DAY 5)

The patient should be instructed to refrain from eating and avoid alcohol as well as opioid and narcotic analgesics the day of the baseline visit (after midnight) , as well as benzodiazepines within 2 hours of the intranasal administration. For visits in the afternoon, patients may have a light meal in the morning no less than 3 hours before the study visit.

Upon arrival, the patient will be administered the SDQ, the HAM-D6, the MADRS, the CGI-I, the CGI-S, and the CHRT. Following completion of these scales the procedures listed in Table 3 should be completed.

The procedures for administration of ketamine and dispensation of blinded study drug will be the same as in section I.1.d and the Manual of Operations for the study.

#### I.1.h. VISIT 5 (DAY 8)

The patient should be instructed to refrain from eating and avoid alcohol as well as opioid and narcotic analgesics the day of the baseline visit (after midnight), as well as benzodiazepines within 2 hours of the intranasal administration. For visits in the afternoon, patients may have a light meal in the morning no less than 3 hours before the study visit.

Upon arrival, the patient will be administered the SDQ, the HAM-D6, the MADRS, the CGI-I, the CGI-S, and the CHRT. Following completion of these scales, the procedures listed in Table 3 should be completed.

The procedures for administration of ketamine and dispensation of blinded study drug will be the same as in section I.1.d. , and the Manual of Operations for the study.

I.1.i. VISIT 6 (DAY 11)

The patient should be instructed to refrain from eating and avoid alcohol as well as opioid and narcotic analgesics the day of the baseline visit (after midnight), as well as benzodiazepines within 2 hours of the intranasal administration. For visits in the afternoon, patients may have a light meal in the morning no less than 3 hours before the study visit.

Upon arrival, the patient will be administered the SDQ, the HAM-D6, the MADRS, the CGI-I, the CGI-S, and the CHRT. Following completion of these scales, the procedures listed in Table 3 should be completed.

The procedures for administration of ketamine and dispensation of blinded study drug will be the same as in section H.1.d. , and the Manual of Operations for the study.

I.1.j. VISIT 7 (DAY 14)

The patient should be instructed to refrain from eating and avoid alcohol as well as opioid and narcotic analgesics the day of the baseline visit (after midnight), as well as benzodiazepines within 2 hours of the intranasal administration. For visits in the afternoon, patients may have a light meal in the morning no less than 3 hours before the study visit.

Upon arrival, the patient will be administered the SDQ, the HAM-D6, the MADRS, the CGI-I, the CGI-S, and the CHRT. Following completion of these scales, the procedures listed in Table 3 should be completed.

The procedures for administration of ketamine and dispensation of blinded study drug will be the same as in section H.1.d. , and the Manual of Operations for the study.

I.1.k. VISIT 8 (DAY 17)

Upon arrival, the patient will be administered the SDQ, the HAM-D6, the MADRS, the CGI-I, the CGI-S, and the CHRT. Following completion of these scales, the procedures listed in Table 3 should be completed.

I.1.l. VISIT 9 (DAY 21)

The patient should be instructed to refrain from eating and avoid alcohol as well as opioid and narcotic analgesics the day of the baseline visit (after midnight), as well as benzodiazepines within 2 hours of the intranasal administration. For visits in the afternoon, patients may have a light meal in the morning no less than 3 hours before the study visit.

Upon arrival, the patient will be administered the SDQ, the HAM-D6, the MADRS, the CGI-I, the CGI-S, and the CHRT. Following completion of these scales, the procedures listed in Table 3 should be completed.

The procedures for administration of ketamine and dispensation of blinded study drug will be the same as in section H.1.d. , and the Manual of Operations for the study.

#### I.1.m. VISIT 10 (DAY 23)

Upon arrival, the patient will be administered the SDQ, the HAM-D6, the MADRS, the CGI-I, the CGI-S, and the CHRT. Following completion of these scales, the procedures listed in Table 3 should be completed.

#### I.1.n. VISIT 11 (DAY 28)

Upon arrival, the patient will be administered the SDQ, the HAM-D6, the MADRS, the CGI-I, the CGI-S, and the CHRT. Following completion of these scales, the procedures listed in Table 3 should be completed.

#### I.1.o. EARLY TERMINATION VISIT

If a patient is terminated from the study before completion, but after at least one dose of ketamine and/or study drug, the procedures listed in Table 3 for Visit 11 (Day 28) should be completed.

#### I.1.p. END OF STUDY TREATMENT ADMINISTRATION

At the end of double-blind treatment (Day 28), both patients and clinicians will be asked to guess treatment assignment.

#### I.1.q. POST-STUDY FOLLOW-UP

Patients who are non-responders at the completion of Visit 11 (Day 28) will be offered a referral for treatment.

#### I.1.r. PATIENT RECRUITMENT

Patients will be recruited through advertisement, as well as clinician referral and self-referral. Self-referred patients will call the study sites and will be screened over the phone by the study coordinators. Those deemed potentially eligible will be scheduled for a screening visit with one of the study physicians at the sites. Based on clinical and human subject protection considerations, a potential subject will, under no circumstance, be advised to taper his/her current medication regimen prior to the screening visit.

Participants will also be recruited through physician referral. Each site will recruit subjects via referral from primary care and specialty clinics from the communities surrounding each study site. Each site will utilize the experience of the MGH CTNI to conduct outreach activities to community organizations, colleges and other resources. Sites will regularly collaborate on strategies to recruit women and minorities, and sites will employ strategies specific to their local community, in ways that are culturally sensitive and specific to the local minority population. Retention will be enhanced with fair reimbursement (as deemed appropriate by the local IRB) for participants’ time.

Assessments and procedures within the study visits will occur as shown in Table 3. A summary description of each data collection instrument is provided later in this section.

## 1.2. PROCEDURES

### 1.2.a. LABORATORY/DIAGNOSTIC PROCEDURES

Once the patient has signed the informed consent document, the urine pregnancy and toxicity test will be performed at screen and baseline visits. 12 lead ECGs will be measured at the screen visit and at visits 4,5,6,7 and 9 as required by the physiological monitoring procedures in the Manual of Operations . A Chemistry and CBC will also be obtained at the screening visit, and at Visits 7 and 11. If TSH is high, subject may be tested for T4 at the request of the PI. Weight, oral temperature, and seated and supine pulse and blood pressure (Vital Signs) will be recorded at each visit. Height is recorded at the Screening Visit only. (BMI is calculated automatically in the EDC). At the screen visit, Visit 7 and at Visit 11, patients will have a physical examination. The laboratory tests required are listed in Table 4, below. Laboratory tests will be performed at the site, and each site will provide their laboratory normal to the coordinating center.

**TABLE 4– LABORATORY TESTS**

Laboratory Test	Frequency
CBC	Screen, Visit 7, Visit 11
Chemistry (Total bilirubin, AST, ALT, GGT, ALK Phosphatase, Creatinine, BUN/Urea, Glucose, Uric Acid)	Screen, Visit 7, Visit 11
TSH, HbA1c	Screen
Pregnancy Test	Screen, Visit 1
Urine Tox Screen	Screen, Visit 1

### 1.2.b. BLINDING PROCEDURES

Individual treatment codes, indicating the treatment randomization for each randomized patient, will be available to the investigator(s) or site pharmacists from a member of the MGH CTNI unblinded staff. The treatment code must not be broken except in medical emergencies when the appropriate management of the patient necessitates knowledge of the treatment randomization. The investigator documents and reports the action to MGH CTNI study staff, in accordance with the procedures in the Manual of Operations, without revealing the treatment given to the patient to MGH CTNI blinded staff. Treatment codes will not be broken for the planned analyses of data until all decisions on the evaluability of the data from each individual patient have been made and documented.

### I.2.C. OUTCOME AND SAFETY MEASURES

#### I.2.c.1. OUTCOME MEASURES

Symptom improvement will be evaluated by assessing changes in the primary outcome measure, the self-rated Symptoms of Depression Questionnaire (SDQ) (Pedrelli et al, 2014). Brexpiprazole has shown in recent studies to have significant benefits in domains such as irritability, anger, anxiety, and nervousness. These domains are not captured or are only partially captured by standard scales such as HAM-D or MADRS. In a recent study of NSI-189, the SDQ slightly outperformed the MADRS in detecting a change over placebo because of the broader symptom net cast by the SDQ.

Secondary outcome measures include the HAM-D6, which has shown greater sensitivity to change and greater effect sizes compared to the longer, multidimensional versions of the HAM-D (e.g., HAM-D-17 and HAM-D-28) (Faries et al, 2000; Bech et al, 2010), the MADRS and the CGI-S and CGI-I (Guy, 1976).

#### I.2.c.2. SAFETY MEASURES

Vital signs will be obtained at every visit. At screening and at visits 1, 4, 5, 6, 7 and 9, digital ECGs will be obtained after the patient has been resting in a semi-recumbent position for at least 10 minutes. All digital ECGs will be documented by recording date, time, heart rate, QRS duration, PR interval, RR interval, QT interval, and QTcF interval. QTcF intervals will be calculated using the Fridericia formula (Puddu et al 1988). If indicated, additional ECG assessments can be made at the discretion of the investigator. The investigator will judge the overall interpretation as normal or abnormal. If abnormal, it will be decided as to whether or not the abnormality is clinically significant or not clinically significant and the reason for the abnormality will be recorded on the eCRF. Abnormal values shall not be recorded as AEs unless deemed clinically significant.

The patient's blood pressure will be measured a total of three times at both the screen and baseline visits (prior to randomization), with each measurement taken at least 15 minutes after the previous measure. If two out of three measurements are within the range for inclusion at each visit (see

Exclusion 17a and 17b), the patient will be considered to have met the enrollment criteria for normal blood pressure. The baseline blood pressure should be measured within 1.5 hours prior to randomization.

At the screen visit and the baseline visit (Visit 1) and at Visit 7 and Visit 11, patients will have their blood drawn for Chemistry and CBC testing. At the screen visit, patients will also have TSH and HbA1c measured. At the screen visit and at Visit 7 and Visit 11, patients will have a physical examination.

The presence of any side effect or adverse event will be carefully documented at screen and at every subsequent visit covering events since the last visit. Reasons for premature discontinuation, including intolerable side effects, will be recorded.

#### I.2.d. STUDY INSTRUMENTS

The following instruments will be administered according to the schedule in Table 3:

##### I.2.d.1. DIAGNOSTIC INSTRUMENTS

**Structured Clinical Interview for DSM-5 (SCID 5):** The SCID, administered by the clinician, includes modules aimed at diagnosing possible Axis I disorders. Questions here are asked exactly as written, and each is based on the individual criteria from DSM-5.

**Massachusetts General Hospital Antidepressant Treatment Response Questionnaire (MGH ATRQ)** (Fava and Davidson, 1996; Fava, 2003): This is a clinician assisted questionnaire that examines the antidepressant treatment history, using specific anchor points to define the adequacy of both dose and duration of each antidepressant trial, as well as the degree of symptomatic improvement obtained with each trial. This questionnaire, which has been validated, allows for the determination of treatment resistance in depression (Chandler et al, 2010).

**Reproductive Lifecycle and Hormone Questionnaire (RLHQ)** (Freeman et al, 2013). This is a standard brief questionnaire implemented systematically at baseline in clinical trials for MDD to assess reproductive lifecycle status and the use of exogenous hormones. This study will use Modules 1 and 2 in all women, and add Module 3 (menstrual cycle tracking) in applicable women.

##### I.2.d.2. EFFICACY MEASURES

**Symptoms of Depression Questionnaire (SDQ)** (Pedrelli et al, 2014): This validated self-rating instrument has 44 items on a scale of 1-6, measuring multiple depressive symptom domains. The time frame for this scale is the past 3 days.

**6 and 17-item Hamilton Rating Scale for Depression (HAM-D6)(HAM-D17)** (Hamilton, 1960, 1967): This instrument is completed with a structured interview guide developed by Per Bech by the clinician based on his/her assessment of the patient's symptoms (Bech et al, 1986). This structured interview has been validated in the DUAG studies for use with time frames shorter than one week

(Gram, 2008). The HAM-D6 has been shown greater sensitivity to change and greater effect sizes compared to the longer, multidimensional versions of the HAM-D (HAMD-17 and HAMD-28) (Faries et al, 2000; Bech et al, 2010). The time frame for this scale is the past 24 hours. Only once, at the baseline visit (Visit 1), will the 17-item version of the HAM-D be administered, in order to examine for the presence of anxious MDD (which is based on the anxiety somatization subscale of the HAM-D17), with the time frame of the past 3 days.

**Clinical Global Impressions–Severity (CGI-S) and Clinical Global Impressions–Improvement (CGI-I) scales** (Guy, 1976): These clinician-rated scales rate the severity of the disorder and the global improvement since beginning of the study. The time frames for these two scales are the past 3 days.

**Montgomery-Asberg Depression Rating Scale (MADRS)** (Montgomery and Asberg, 1979): This 10-item clinician-rated instrument measures depression severity. It will be administered with a structured interview guide. The time frame for this scale is the past 3 days.

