## E. STUDY RATIONALE

Primary Aim: The primary objective is to investigate whether brexpiprazole (initial dose .5 mg/day titrating to 3 mg/day over 21 days) is superior to placebo when combined with intranasal ketamine in the acute treatment of patients with TRD at two weeks (Day 14), when added to ongoing and stable antidepressant therapy with respect to the study primary outcome measure [change in the SDQ total score].

Secondary Aim 1: The secondary objective #1 is to investigate whether brexpiprazole (initial dose .5 mg/day titrating to 3 mg/day over 21 days) is superior to placebo when combined with intranasal ketamine in the acute treatment of patients with TRD within 48 hours (Day 2), when added to ongoing and stable antidepressant therapy with respect to the study primary outcome measure [change in the SDQ total score].

Secondary Aim 2: The secondary objective #2 is to investigate whether brexpiprazole (initial dose .5 mg/day titrating to 3 mg/day over 21 days) is superior to placebo when combined with intranasal ketamine in the acute treatment of patients with TRD at four weeks (Day 28), when added to ongoing and stable antidepressant therapy with respect to the study primary outcome measure [change in the SDQ total score].

Secondary Aim 3: The secondary objective #3 is to investigate whether brexpiprazole (initial dose .5 mg/day titrating to 3 mg/day over 21 days) is superior to placebo when combined with intranasal ketamine in the acute treatment of patients with TRD at four weeks (Day 28), when added to ongoing and stable antidepressant therapy with respect to the rates of sustained response [50% or greater reduction in the MADRS total score].

Secondary Aim 4: The secondary objective #4 is to investigate whether brexpiprazole (initial dose .5 mg/day titrating to 3 mg/day over 21 days) is superior to placebo when combined with intranasal ketamine in the acute treatment of patients with TRD at Day 2, Day 14, and Day 28, when added to ongoing and stable antidepressant therapy with respect to the study secondary outcome measures [MADRS, HAMD-6, CGI-S, CGI-I].

Secondary Aim 5: The secondary objective #5 is to characterize the safety and tolerability of brexpiprazole or placebo treatment during the acute, 4-week treatment period.

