#### I.1.a. SCREENING PHASE

The screening period will range from a minimum of 7 days to a maximum 28 days. The purpose is to ensure that only appropriate patients are entered into the study. The investigator will determine that the patients meet eligibility criteria and will collect the demographic and medical data permitting full characterization of the patients. The screening period is also designed to ensure that any prohibited pharmacotherapy is washed out. Benzodiazepine therapy is allowed per the requirements in Appendix I. The screening period begins when informed consent is signed. Screening evaluations are to be conducted as outlined in the Study Schedule (

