#### I.1.d. BASELINE VISIT (VISIT 1) (DAY 0)

The patient should be instructed to refrain from eating and avoid alcohol as well as opioid and narcotic analgesics the day of the baseline visit (after midnight), as well as benzodiazepines within 2 hours of the intranasal administration. For visits in the afternoon, patients may have a light meal in the morning no less than 3 hours before the study visit.

Upon arrival, the patient will be administered the SDQ, the 17-item Hamilton Rating for Depression (HAM-D-17), the MADRS, the CGI-I, the CGI-S, and the CHRT by the site rater.

Upon completion of all study-related inclusion procedures as listed in Table 3 and upon the investigator's confirmation that the patient still meets all of the study inclusion criteria and none of the exclusion criteria, the patient may be randomized.

All subjects will be dispensed brexpiprazole or placebo, as well as 40 mg of ketamine administered intranasally. The study drug ( brexpiprazole or placebo) should be taken by the patient before ketamine administration. Detailed instructions for ketamine dose preparation will be provided to the pharmacist in an additional guidance document. Storage conditions should be followed according to the package insert. Dosing procedures will be provided to the clinical unit in a separate document.

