## N. DATA ANALYSIS

To analyze the primary outcome data, we will use a linear mixed model for the observations taken at baseline, and subsequent visits, with terms for visit, and visit\*treatment for visits other than baseline, the primary contrast of interest being the difference between the two weeks (Day 14) value for active treatment and placebo. To address missing data, we will use all available data and use a restricted maximum likelihood estimation procedure, as implemented by SAS Proc MIXED. The model will include a site, a site\*time effect and a site\*time\*treatment interaction. The latter will be removed if not significant. Number of comorbid medical and psychiatric disorders and duration of illness, as measured prior to randomization, will be included as covariates. For the continuous secondary efficacy variables, the same approach as for the primary efficacy variable will be used for the analysis.

Power analysis: the sample size was chosen to ensure 80% power to detect an effect size of 0.8 on the SDQ between brexpiprazole plus intranasal ketamine treatment and placebo at a two-sided 0.05 significance level. This assumes the randomization of 52 subjects (26 subjects per arm).

O. PROTOCOL SIGNATURE PAGE

I have read this protocol and agree to adhere to the requirements. I will provide copies of this protocol and all pertinent information to the study personnel under my supervision. I will discuss this material with them and ensure they are fully informed regarding the conduct of the study according to 21 CFR parts 50, 54, 56 and 812, 45 CFR 46, to GCP as described in ICH guideline E6 and to hospital Institutional Review Boards.

\_\_\_\_\_  
Clinical Site

\_\_\_\_\_  
Principal Investigator Signature

\_\_\_\_\_  
Date

\_\_\_\_\_  
Principal Investigator  
Printed Name

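### Section N's model, which treats baseline as a response, does not suit CGI-I (reference visit not named, yet rated at Visit 1) or HAM-D6 (no Visit 1 rating)

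*Combined protocol and SAP*

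**What the plan says.** Section N states that "we will use a linear mixed model for the observations taken at baseline, and subsequent visits", with a visit term and visit-by-treatment terms only after baseline. Baseline is therefore one of the responses, not a covariate. The target is "the primary contrast of interest being the difference between the two weeks (Day 14) value for active treatment and placebo". Section N then adds: "For the continuous secondary efficacy variables, the same approach as for the primary efficacy variable will be used for the analysis". It does not list those variables and names no covariance structure. Secondary Aim 4 in section E tests superiority at Days 2, 14 and 28 "with respect to the study secondary outcome measures [MADRS, HAMD-6, CGI-S, CGI-I", and F.2 treats the same four scales as scores that should fall more on brexpiprazole.

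**CGI-I.** Section I.2.d.2 says of the two CGI scales: "These clinician-rated scales rate the severity of the disorder and the global improvement since beginning of the study". No visit is named. Section I.1.a says "The screening period begins when informed consent is signed", so the start of the study could mean screening. Table 3 has no CGI-I at screening and has it from Visit 1 onward. Section I.1.d lists it among the ratings made on arrival, before randomisation: "the MADRS, the CGI-I, the CGI-S, and the CHRT by the site rater".

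**HAM-D6.** Table 3 and section I.1.e start it at Visit 2: "Upon arrival, the patient will be administered the SDQ, the HAM-D6, , the CGI-I, the CGI-S, and the CHRT". At Visit 1 only the HAM-D17 is given, on a 3-day frame and to identify anxious depression; the HAM-D6 uses 24 hours (I.2.d.2). Nothing says that a six-item baseline will be scored from the HAM-D17.

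**The concern.** A model with baseline as a response gains from a baseline that varies between patients and correlates with later scores. An improvement rating made at its own reference visit does neither: every patient scores no change. An analyst who applies Section N literally to CGI-I would then either meet a singular covariance and have to choose another structure after seeing the data, or fit a simpler structure that runs without warning and gives a standard error that is too small. For HAM-D6 there is no baseline value to enter, so two analysts could reasonably proceed differently, one with no adjustment and one with a score derived from the HAM-D17. These are two of the four named secondary scales.

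**Working it through.** **The plan's own figure.** Section N's power statement (effect size 0.8, two-sided 0.05, 26 per arm, 80%) reproduces: a two-sample t-test gives 80.7%. It concerns the SDQ, which is rated at Visit 1, so nothing below changes it. The plan gives no figure for CGI-I or HAM-D6.

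**CGI-I: inputs.** From the documents: 26 per arm; 11 visits (Visit 1 plus 10 later ones); baseline as a response; visit-by-treatment after baseline only; REML. Assumed, because the documents give no values: SD 1 after Visit 1 and between-visit correlation r of 0.3 to 0.7.

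**CGI-I, constant Visit 1 value, unstructured covariance.** The Visit 1 variance is 0. In a numerical check the 11 x 11 covariance matrix had rank 10, so the fit is singular. This is visible at fitting.

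**CGI-I, constant Visit 1 value, compound symmetry.**
- True SE of the Day 14 difference: sqrt(2/26) = 0.277.
- The model pools one zero-variance visit with ten of variance 1, so the fitted variance is about 10/11 = 0.909.
- Of the 55 visit pairs, 45 have covariance r and 10 have covariance 0. The fitted correlation is about (45r/55)/(10/11) = 0.9r.
- The model takes the Visit 1 score to be informative and credits a baseline adjustment: model SE = sqrt[(2/26)(10/11)(1 - (0.9r)^2)].

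This gives 0.255, 0.236, 0.223 and 0.205 for r = 0.3, 0.5, 0.6 and 0.7. At r = 0.6, variance pooling alone lowers the SE from 0.277 to 0.264; the unearned baseline adjustment takes it to 0.223.

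Simulation (8,000 trials per setting, no treatment effect, no missing data, no site terms or Section N covariates, t with 50 df), Day 14:

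| r | Model SE | Empirical SE | Type I error |
|---|---|---|---|
| 0.3 | 0.254 | 0.274 | 6.1% |
| 0.5 | 0.235 | 0.275 | 8.7% |
| 0.6 | 0.222 | 0.275 | 10.4% |
| 0.7 | 0.205 | 0.276 | 13.9% |

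As a check, the critical value 2.009 times the SE ratio (0.222/0.275 = 0.807 at r = 0.6) is 1.62, whose two-sided normal tail is 10.5%. Repeat simulations gave 6.8-7.1%, 8.4-9.5%, 10.2-11.3% and 14.1-15.0%, hence about 6-15% overall.

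**Sensitivity to the fitted structure.** With an AR(1) fit, type I error is 6.0-7.0% at Day 14 and 5.8-6.7% at Day 28, but 6.3-12.2% at Day 2, which Aim 4 also tests.

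**CGI-I, Visit 1 scores vary (screening as reference).** Compound symmetry, Day 14, by Visit 1 SD relative to later SD:

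| r | 0.25 | 0.5 | 0.75 | 1.0 |
|---|---|---|---|---|
| 0.3 | 6.4% | 5.6% | 5.1% | 4.5% |
| 0.5 | 7.2% | 6.4% | 5.3% | 4.7% |
| 0.6 | 8.8% | 6.8% | 5.2% | 4.4% |
| 0.7 | 10.3% | 7.8% | 5.6% | 4.7% |

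**HAM-D6.** The planned contrast is a between-arm difference in visit values, so randomisation keeps it valid without a baseline. The cost is precision. Let r be the correlation of a same-frame baseline with the outcome, and let the derived 3-day score correlate k = 0.7-0.9 with the 24-hour score (assumed). Then SE without baseline / SE with derived baseline = 1/sqrt(1 - (kr)^2):
- r = 0.3: 1.02-1.04
- r = 0.5: 1.07-1.12
- r = 0.7: 1.15-1.29

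Against a perfectly matched baseline (k = 1) the ratios are 1.05, 1.15 and 1.40.

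**The case against.** The CGI-I inflation needs several things at once: Visit 1 as the reference, the same score recorded for everyone, that score kept in the model, and a covariance that assumes equal variances. The documents fix none of them. The schedule even gives some support to screening as the reference, since rating improvement at Visit 1 has little purpose otherwise. An unstructured fit would fail openly, so the analyst would be warned. The simulations also leave out site terms, covariates and missing data. Finally, Section N covers continuous variables without listing them, so including CGI-I is an inference. All of this stands, and it makes the CGI-I result conditional. It does not remove the point: no other method is given for CGI-I, the reference visit is open, and an open failure still leaves the replacement structure to be chosen after the data are seen.

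On HAM-D6, a reader might infer that the scale has no usable baseline and that its analysis is invalid. The documents do not support that. REML on all available data can be fitted from Visit 2, the randomised contrast is unbiased by the missing rating, and the HAM-D17 is collected at Visit 1. Using a derived score is an efficiency choice, and for correlations of 0.3-0.5 the gain is small.

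**Conclusion.** The point holds in conditional form and is minor. Section N's baseline-as-response model does not suit CGI-I or HAM-D6, and the plan does not say what to do instead. For CGI-I with Visit 1 as reference and a constant score retained, the model is either singular or, under compound symmetry, anti-conservative: about 6-15% at Day 14 against a nominal 5%, for assumed correlations of 0.3-0.7. With screening as reference, the error returns to about 5% once the Visit 1 SD approaches the later SD. For HAM-D6 the loss is precision only, a factor of about 1.02-1.29 in the standard error under assumed correlations.

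A reader might also infer that the trial as planned has an inflated CGI-I error rate, or that the primary result is at risk. Neither follows. The first depends on choices that the documents leave open. As for the second, SDQ, MADRS and CGI-S all have ordinary Visit 1 ratings.

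**What to change.** 1. **CGI-I.** State that Visit 1 is the reference visit. Leave the Visit 1 CGI-I out of the response vector. Analyse post-baseline CGI-I with Visit 1 CGI-S, by visit, as covariate. Use a covariance that lets variances differ by visit: unstructured, with heterogeneous compound symmetry as the named fallback.
2. **HAM-D6.** Analyse post-baseline HAM-D6 with the six-item score from the Visit 1 HAM-D17, by visit, as covariate, and note the 3-day against 24-hour recall. This assumes that the six items are among the 17; the scoring rule should be written down, since the documents do not give it.

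**Performance.** In simulations of the CGI-I fix (6,000 trials per setting, assumed CGI-S correlation 0.1-0.2), unstructured gave type I error of 4.6-5.6% across Days 2, 14 and 28. The fallback gave 4.6-5.6% when the true correlation was compound symmetric and 3.6-6.1% when it was AR(1).

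**Cost.** Analysis wording only. CGI-S and HAM-D17 are already collected at Visit 1, and the Visit 1 CGI-I becomes unnecessary. Ten post-baseline visits give 10 x 11/2 = 55 covariance parameters for 52 patients, so the fallback may well be used; its upper end of 6.1% is not perfect control. If ratings have already been made against screening, the document should say so; steps 1 and 2 still apply apart from the naming of the reference visit.
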